12.10 ECOG Performance Status

ECOG performance status will be assessed at Screening, and Week 3 (Day 17+-2 days) at Cycles 1-4, Day 1 of Cycles 5+, and 28 days Safety Follow-up. The ECOG performance status categories (6-point scale) are as follows:

| Grade | ECOG |
|-------|---|
| 0 | Fully active, able to carry on all pre-disease performance without restriction. |
| 1 | Restricted in physically strenuous activity but ambulatory and able to carry out work of a light or sedentary nature, e.g., light housework, office work. |
| 2 | Ambulatory and capable of all selfcare but unable to carry out any work activities. Up and about more than 50% of waking hours |
| 3 | Capable of only limited self-care, confined to bed or chair more than 50% of waking hours |
| 4 | Completely disabled. Cannot carry on any self-care. Totally confined to bed or chair |
| 5 | Dead |

ECOG will be summarized by expansion group using shifts from screening to the patient’s “worst” (i.e., highest number) ECOG score during the post-baseline study period and the last ECOG score taken post-baseline.

ECOG assessments will be included in patient listings.

12.11 Echocardiogram (ECHO) or Multigated acquisition (MUGA)

From the ECHO or MUGA scans, the LVEF (%) results are reported for the following time points:

- Screening.

- Treatment: An ECHO or MUGA scan (whichever was performed during screening) should be reported for 7 days from Cycle 3 Day 1, Cycle 5 Day 1 and Day 1 of every cycle thereafter
- Safety Follow-Up: An ECHO or MUGA scan (whichever was performed during screening) should be reported for the Safety Follow-Up visit if not performed in the previous 14 days.
- Long Term Follow Up (if applicable): An ECHO or MUGA scan (whichever was performed during screening) should be reported for each Long-Term Follow-Up visit.

Ejection Fraction percentages, LVEF (%), will be provided in table format by timepoint and by change from baseline summaries using descriptive summary statistics (n, mean, SD, median, range).

ECHO or MUGA test results to assess left ventricular ejection fraction (LVEF) will be presented in the patient listings.

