2.2.2. Endpoints

2.2.2.1. Primary Endpoints

- Frequency of AEs and SAEs, as well as changes from baseline in vital signs, clinical laboratory parameters, physical examination findings, ECHO/MUGA, and ECG results across all treatment cycles and groups.

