6.16. CARDIOTOXICITY BIOMARKERS FOR PHASE 2A EXPANSION GROUPS ONLY

6.16.1. General Guidance

Cardiotoxicity is the highest risk in cumulative doxorubicin doses with a lifetime dose should not exceed 450-550 mg/m² of body surface area ([PDR.net](#)). Cardiotoxicity has been defined as a decrease in the LVEF of greater than ten percentage points to a value below the average reference value (EF 53%). However, the LVEF measurements taken after doxorubicin exposure were not predictive of later cardiotoxicity ($p=0.075$) ([Sawaya 2012](#)). Combining ECHO, Troponin I and BNP serum levels have been used to monitor cardiotoxicity, i.e., elevated levels of troponin I (>30 pg/mL) and BNP (>100 pg/mL), and a decrease in LVEF from baseline ([Skovgaard 2014](#)).

- Other markers have been shown to have predictive values:
 - Serum topoisomerase 2b levels ≥ 0.5 ng/ μ g are associated with LVEF decline ($p=0.001$). The log-rank test showed that patients expressing a higher Top2b level (≥ 0.5 ng/ μ g) had a higher probability of LVEF decline over time ($p=0.001$) ([Win 2018](#)).
 - Myeloperoxidase, patients with elevated MPO levels (>350 μ g/L) experienced a marked increased cardiac risk (adjusted hazard ratio [HR] 2.25 [1.32 to 3.82]; $p=0.003$) ([Baldus 2003](#)).
- Serum samples will be taken around the time of the ECHO/MUGA.

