7.5.4. Management of Potential Myocardial Toxicity and ECHO / MUGA Changes

SQ3370 should be stopped at the first sign of impaired cardiac function. ECG changes such as dysrhythmias or conduction delays may be indicative of anthracycline-induced cardiomyopathy. A 10% decline in LVEF to below the lower limit of normal or an absolute LVEF of 45% or a 20% decline in LVEF at any level is indicative of deterioration in cardiac function. In general, if test results indicate deterioration in cardiac function associated with SQ3370, the benefit of continued treatment should be carefully evaluated against the risk of producing irreversible cardiac damage. Acute life-threatening arrhythmias have been reported to occur during or within a few hours after conventional Dox administration.

Other events such as myocardial infarction, anginal symptoms, elevated serum troponin-T, or symptoms or signs of new congestive heart failure should be reported to the Sponsor immediately and Investigational Product administration should be halted. The patient should be evaluated and if there appears to be significant evidence of myocardial injury, study treatment should be discontinued permanently.

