8.4 Data Presentation Conventions

Continuous safety variables (e.g., clinical laboratory values and vital signs) will be listed to the same precision as the source data. Derived variables will be calculated and listed using the same precision as the value(s) from which they were derived.

For the tabular reporting of descriptive statistics:

- Continuous variables: the same number of decimal places as in the raw data will be presented when reporting minimum and maximum, 1 more decimal place than in the raw data will be presented when reporting mean and median, and 2 more decimal places than in the raw data will be presented when reporting SD.
- Categorical/discrete variables: the frequency count and the percentage (of available data) for each class of the variable will be presented and will be displayed in the form XX (XX.X%) where the percentage is in parentheses. All percentages will be presented to 1 decimal place, unless otherwise specified. Percentages equal to 100 will be reported as 100% and percentages will not be presented for zero frequencies. Unless otherwise specified, percentages will be calculated based on the number of patients specified by the appropriate population definition.
- Date variables: formatted as DDMMYY for presentation. Time will be formatted in military time as HH:MM for presentation.

Extra measurements (such as unscheduled or repeat assessments) will not be included in summary tables but will be included in patient listings. They will be used in summary tables which are not 'time specific', for example, summaries of minimum maximum, first, last, average post dose values.

All tables, listings, figures will be produced in landscape orientation using Arial 9-point font. Output files will be created in rich text file (RTF) format.

Missing or invalid data will be generally treated as missing, not imputed, unless otherwise stated (see Section 9.5).

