9. GENERAL CONSIDERATIONS FOR DATA ANALYSES

The listings, figures and summary tables for the disposition, baseline characteristics, study drug administration, safety, and efficacy data will be the responsibility of the study Biostatistician at Vantage Data Designs.

The currently supported version of SAS software (9.4 or later) will be used to perform all data analyses. The actual SAS version used will be presented in the Clinical Study Report.

All data in the database will be presented in the data listings. Unless otherwise stated, all listings will be sorted by Phase 2A expansion group, patient number, and assessment date/time.

Unless otherwise stated, continuous variables will be summarized using descriptive statistics including number of non-missing observations, mean, standard deviation, median, minimum and maximum values. Categorical variables will be summarized with frequency counts and percentages. The population size (N for sample size and n for available data) and the percentage (of available data) for each class of the variable will be presented.

In general, only data from nominal protocol scheduled visits will be included in the summary tables. They will be used in summary tables which are not 'time specific', for example, summaries of first, last, minimum, maximum, and average post dose values. Data from unscheduled visits will not be included in the summary tables but will be included in the listings.

The Efficacy Evaluable analysis set will be the primary basis for the response efficacy endpoints and the Full Analysis Set for time-to-event endpoints (time-to-event has 'censoring' rules in place for missing data). The Safety analysis set will be used for the safety summaries.

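### Phase 2a SAP 12.11 gives no count of patients whose measured LVEF ever met a protocol 7.5.4 threshold, and its by-visit statistics cannot supply one

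*SAP*

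**What the plan says.** Protocol 2.2.2.1 includes in the Phase 2a primary endpoint "changes from baseline in vital signs, clinical laboratory parameters, physical examination findings, ECHO/MUGA, and ECG results across all treatment cycles and groups". Phase 2a SAP 12.11 lists the scan timepoints and then plans one type of table: "Ejection Fraction percentages, LVEF (%), will be provided in table format by timepoint and by change from baseline summaries using descriptive summary statistics". The statistics named are n, mean, SD, median and range. Individual results go to listings. At the end of treatment a scan "should be reported for the Safety Follow-Up visit if not performed in the previous 14 days".

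Protocol 7.5.4 gives numeric signs of cardiac deterioration: "A 10% decline in LVEF to below the lower limit of normal or an absolute LVEF of 45% or a 20% decline in LVEF", the last of these at any level. SAP 12.11 does not refer to them.

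On unscheduled scans, SAP 8.4 says: "Extra measurements (such as unscheduled or repeat assessments) will not be included in summary tables but will be included in patient listings". It makes an exception for tables that are not tied to a timepoint, such as "summaries of minimum maximum, first, last, average post dose values". SAP 9 repeats the main rule: "Data from unscheduled visits will not be included in the summary tables". SAP 12.11 defines no LVEF summary of the excepted kind.

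Elsewhere, protocol 7.1.2 and 7.1.2.2 make potential myocardial toxicity, including a significant fall in ejection fraction on ECHO or MUGA, an adverse event of special interest (AESI). SAP 12.5 tabulates AESIs. The same SAP plans worst-grade shifts for hematology (12.7.1) and a shift to the worst post-baseline score for ECOG (12.10).

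**The concern.** Cardiotoxicity is the known cumulative risk of doxorubicin and the stated reason for the scans (protocol 6.8). The natural safety question is how many patients in each group had a decline that meets the protocol's own numbers. Columns by visit do not answer it. A lasting fall in one patient recurs in several columns, so columns cannot be added. Within a column, mean, SD, median and range do not fix how many patients crossed a threshold.

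The AESI table counts patients, but it depends on the investigator ticking a box, and protocol 7.1.2.2 attaches no number to the fall. Listings allow a hand count, but only after the reader has decided what 10%, 20% and 45% in 7.5.4 mean. Different readers could then report different counts for a measure in the primary endpoint.

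**Working it through.** The plan states no figure to reproduce. The check is whether the planned statistics determine the patient count.

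**Within one visit column.** Constructed integer changes from baseline in LVEF points, not trial data. SD = √[(Σx² − (Σx)²/n)/(n − 1)].

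- n = 20, set 1: −18, −9, −8, −6, −5, −5, −5, −4, −4, −1, −1, 0, 0, 1, 2, 2, 2, 3, 8, 8. One fall of 10 points or more.
- n = 20, set 2: −18, −10, −10, −10, −4, −3, −2, −2, −2, −1, −1, 0, 1, 1, 2, 2, 3, 3, 3, 8. Four such falls.
- Both: Σx = −40, Σx² = 764; mean −2.0; SD = √[(764 − 80)/19] = √36 = 6.00; median −1.0; range −18 to 8.
- n = 11 (one Group 2 arm), set 1: −18, −7, −7, −4, −1, −1, 0, 1, 2, 5, 8. One such fall.
- n = 11, set 2: −18, −10, −4, −1, −1, −1, −1, 0, 1, 5, 8. Two such falls.
- Both: Σx = −22, Σx² = 534; mean −2.0; SD = √[(534 − 44)/10] = √49 = 7.00; median −1.0; range −18 to 8.

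**Across columns.** Take 11 patients and three visits. In case A one patient is down 20 points at all three visits. In case B three different patients are each down 20 points at one visit. Every other change is 0. In both cases every column reads n = 11, mean −20/11 = −1.82, SD = √[(400 − 400/11)/10] = 6.03, median 0, range −20 to 0. The number of patients ever down 20 points is 1 in A and 3 in B.

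**What the range does give.** The lowest value in each column shows whether any scheduled scan reached 45%, and the lowest change shows whether any fall reached 20 points. It does not give the number of patients or show whether the same patient recurs. The first 7.5.4 criterion combines a decline with a value below the lower limit of normal. Separate ranges for value and change may come from different patients, so they need not settle it.

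**The reading of 7.5.4 changes the count.** The cut-off for the first criterion is the lower of (baseline − 10) or (0.9 × baseline) and the lower limit of normal, strictly below the limit where the limit binds. The limit is assumed to be 53% (the reference value in protocol 6.16.1) or 50%.

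| Baseline and criterion | Percentage points | Relative |
|---|---|---|
| 55%, first criterion, limit 50% or 53% | 45% or lower | 49.5% or lower |
| 60%, first criterion, limit 53% | 50% or lower | below 53% |
| 60%, first criterion, limit 50% | below 50% | below 50% |
| 65%, 20% decline | 45% or lower | 52% or lower |

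A change from 55% to 48% therefore meets the first criterion on the relative reading (7/55 = 12.7%) and not on the points reading (7 points).

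**Precision of the added count** (exact Clopper–Pearson 95% intervals; event numbers are illustrative, denominators are the planned sizes of a Group 2 arm, Group 3a and Group 1): 0/11, 0 to 28.5%; 1/11 = 9.1%, 0.2 to 41.3%; 3/26 = 11.5%, 2.4 to 30.2%; 3/46 = 6.5%, 1.4 to 17.9%.

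**The case against.** The SAP delivers the endpoint as worded. The protocol asks for changes from baseline, described, and protocol 8.4.1 asks for no count against a threshold. Section 7.5.4 guides patient management and is not an analysis definition. An ejection-fraction fall that the investigator judges significant is already an AESI, reportable within 24 hours (protocol 7.2) and tabulated. The range exposes the worst scheduled value at each visit, and with 11, 11, 26 and 46 patients the listings make a hand count short. All of this stands. It reduces the gap to the difference between judged and measured declines, and makes the point one of better practice.

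Three stronger readings are tempting, and the documents do not support them.

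- A reader might infer that LVEF falls are counted nowhere. The AESI table contradicts this.
- A reader might infer that patients who stop after a fall drop out of the LVEF tables. A fall seen at a scheduled scan is already in a column, and the Safety Follow-Up scan has its own. Only a fall seen solely at an unscheduled scan is lost to the tables. That requires no later scheduled scan to show it, and a Safety Follow-Up scan that is missed or waived under the 14-day rule. The documents give no basis for a frequency.
- A reader might infer that LVEF is treated worse than laboratory tests, vital signs and QTcF. The minimum and maximum rows for laboratory tests and vital signs are explained by the large number of visits, and the QTcF categories are also counted visit by visit. The fair comparators are the hematology worst-grade shift and the worst-ECOG shift.

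On the wording of 7.5.4, protocol 6.16.1 describes cardiotoxicity in percentage points. That is background text and does not bind 7.5.4, but it favours the points reading.

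**Conclusion.** The point holds as a cheap improvement. For a safety measure in the primary endpoint, the planned outputs give by-visit distributions, listings and investigator-judged events. They do not give the number of patients whose measured LVEF ever met a 7.5.4 criterion, and that number cannot be recovered from the planned statistics: identical columns are compatible with 1 or 4 patients at n = 20, with 1 or 2 at n = 11, and with 1 or 3 patients across three visits. No test, estimate or stopping rule is affected.

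The size shown rests on constructed data. It proves that the count is undetermined and does not predict how far off a reader would be. The cut-offs rest on an assumed lower limit of 50% or 53%. The conclusion also assumes that the table shells, which SAP 8.4 calls part of the SAP and which are not in the documents seen, add no such table.

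**What to change.** In Phase 2a SAP 12.11, keep the by-visit statistics. Add the following per expansion group (Group 2 by arm), using all post-baseline scans including unscheduled and Safety Follow-Up scans:

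- minimum post-baseline LVEF and largest decline from baseline per patient, summarised descriptively;
- number and percentage, with exact 95% CI, of patients who ever meet each 7.5.4 criterion.

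Before database lock, state whether declines are in percentage points (the reading protocol 6.16.1 favours) or relative to baseline, that the 45% criterion means 45% or lower, and which lower limit of normal applies (site value or 53%). Show the count beside the AESI table, so that measured and judged events can be compared. SAP 8.4 already admits unscheduled values to summaries that are not time specific, so no rule has to change.

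The cost is some SAP text and one or two tables from LVEF values already collected, with no new procedure. The Phase 2a SAP is still marked version 0.1. The drawback is small counts with wide intervals.

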12.12 Physical Examination

A physical examination should include a review of the following body systems: constitutional, skin, HEENT (head, eyes, ears, nose, and throat), neck, chest and lungs, cardiovascular, abdomen, neurological, and musculoskeletal, and genitourinary and gynecologic if indicated by the Investigator.

Symptom directed examinations should include an examination of organ systems related to patient symptoms for potential AEs. Any new post-baseline abnormal physical examination findings assessed as clinically significant should be recorded as an AE or SAE.

Physical examinations results will be displayed in patient listings.

12.13 Pregnancy Test

Individual patient data listings will be displayed for pregnancy test results.

13. PHARMACOKINETIC (PK) ANALYSIS

PK in tumor and plasma and binary variable exploratory analyses will be performed by the Shasqi R&D group and/or sponsor PK consultant and is not part of this SAP. A separate PK data analysis plan will be developed prior to the database lock.

14. BIOMARKER ANALYSIS

Immune response will be evaluated based upon summaries of the biomarker data collected as part of the tumor biopsies and by summarizing the PBMC data. These data will be summarized by dose (Phase 1), Expansion Group (Phase 2a), time point measured, and changes over time. Listings of the individual measures will also be provided. Biomarker data analysis will be performed by the Shasqi R&D group and/or sponsor consultant and a separate Biomarker data analysis plan will be developed prior to database lock. .

15. COMMITMENT TO GOOD STATISTICAL PRACTICE

15.1 Definition of Good Statistical Practice

The International Conference on Harmonisation (ICH) Guidance on Statistical Principles for Clinical Trials (ICH E9) implicitly defines good statistical practice. Good statistical practice includes both appropriate statistical designs to minimize bias and to maximize precision of analysis plus operational excellence to assure credibility of results. The scientific design associated with any clinical trial is found in the protocol and in a more detailed pre-specified statistical analysis plan such as this one.

15.2 Data Management and Use of CDISC Standards

Data standards for clinical development of drugs have been defined and are maturing under various initiatives through the Clinical Data Interchange Standards Consortium (CDISC).

Shasqi will use third party vendors for clinical data collection and data analysis. Clinical data will be managed by Novotech (Australian based CRO). and will be captured in electronic case report form (eCRF) by the Medidata RAVE platform. The “raw” data contained in the eCRF clinical database will then be converted into Study Data Tabulation Model (SDTM) datasets per CDISC standards by Novotech. The SDTM datasets will then be utilized in statistical data analysis as the source to create Analysis Data Model (ADaM) datasets. These ADaM data conversions and data analysis will be conducted by Vantage Data Designs.

Other applicable standards include regulatory guidance's from the Food and Drug Administration (FDA), ICH Guidance on the Structure and Content of Clinical Study Reports (ICH E3), and ICH Guidance for Good Clinical Practice (ICH E6).

15.3 Testing/Validation Plan and Software System

Statistical Analysis Software (SAS) version 9.4 or later will be used to analyze the data, create summary tables, patient data listings, and graphical representation of the data. All

SAS computer programs will be validated using industry standard validation procedures including independent quality control programming.

16. STATISTICAL ANALYSIS CHANGES FROM THE PROTOCOL

The analyses described are based on the final clinical study protocol SQ3370-101 Amendment 8 dated November 17, 2022. This SAP supersedes the statistical considerations identified in the protocol. The following table summarizes changes in the SAP versus the protocol:

| SAP | Protocol | Reason |
|-----|----------|--------|
| N/A | N/A | N/A |

18. SCHEDULE OF ASSESSMENTS

Expansion Group 1: Extremity STS

| Study Day | Screening | Treatment | | | | SFTY FU | LTFU | | |
|-----------|-------------------------------|-------------------|--|--------------|-----------------------------------|---------------------------|-----------------------|--|--|
| | | Week 1 | | Week 2 | | | | | |
| | | Day -28 to Day -1 | Day 1 ^A | Day 2/3/4 | Day 5 | | | | |
| Safety | On-Site | On-Site | On-Site | On-Site | Telephone or On-Site ^B | On-site | Variable ^M | | |
| | Informed consent ^C | X | | | | | | | |
| | Medical history | X | | | | | | | |
| | Review Inc/Exc Criteria | X | | | | | | | |
| | Confirm Eligibility | | X | | | | | | |
| | Physical Exam | X | | | | | | | |
| | Symptom-Directed PE | | X ^D | | | X | | | |
| | Vital Signs | X | X | X | X | X | | | |
| | ECHO or MUGA | X | Every other cycle ^E | | | X ^K | | | |
| | Triplicate 12-Lead ECG | X | X ^{D, F} | Cycle 1 Only | Cycle 1 Only | X | | | |
| | ECOG | X | Cycle 2+ | | | X | | | |
| | AE Review | | X | X | X | X | | | |
| | Commed Review | X | X | X | X | X | | | |
| | Hematology & Chemistry | X | X ^D | Cycle 1 Only | X | Cycle 1 Only ^D | X ^D | | |
| | Coagulation & Urinalysis | X | | | | | X ^D | | |
| Labs | Pregnancy Test | X ^G | X ^D | | | | X ^D | | |
| | Serology | X | | | | | | | |
| | Plasma PK | | Cycle 1 & 2 only; see separate PK Schedule | | | | | | |
| | PBMC / ctDNA ^O | | Cycle 1, 2, 3 only | | | | | | |
| | Cardio Tox Biomarkers | X | Every other cycle ^E | | | X | | | |
| | Tumor Biopsy | | Cycle 1, 2, 3 only ^H | | | | | | |
| | CT / MRI & RECIST | X | Every 6 weeks ^I | | | X ^L | X ^N | | |
| IP | Administer SQL70 Biopolymer | | X | | | | | | |
| | Administer SQP33 Protodrug | | X ^J | X | X | | | | |
| Survival | Vital Status | | | | | | X | | |

Notes For EXPANSION GROUP 1: EXTREMITY STS

A - Day 1-5 is typically Monday through Friday, however if the site can accommodate protocol procedures on the weekends Day 1 may start on any day of the week.

B - Day 10 visit may be performed via telephone (using a lab closer to a patient's home) or on-site.
 C - Written informed consent must be obtained prior to any study-specific procedures.
 D - May be performed up to 3 days before the visit.
 E - ECHO/MUGA to be performed every other cycle starting at Cycle 3; may be performed up to 7 days before the visit. Serum sample for cardiotoxicity biomarker analysis is to be collected on the same day.
 F - ECG to be performed pre dose and post dose +30 minutes.
 G - To be collected \leq 7 days prior to Cycle 1 Day 1 for women of child-bearing potential.
 H - Collect biopsy unless the tumor is considered too small to be biopsied; biopsy can be performed during screening and up to 4 days prior to Day 1 for other cycles. Resected tumor samples should be collected at the time of surgery.
 I - May be performed up to 7 days prior to the projected every 6 weeks from C1D1 date presurgical disease re-evaluation.
 J - SQP33 protodrug infusion occurs within 3 hrs \pm 30 mins after receiving SQL70 biopolymer injection.
 K - ECHO or MUGA not required at the Safety Follow-Up visit if performed in the previous 14 days.
 L - CT / MRI & RECIST not required at the Safety Follow-Up visit if performed in the previous 6 weeks.
 M - For up to 2 years after treatment end; collected during routine clinic visits, telephone or e-mail with the subjects/caregivers or referring physician offices.
 N - Until disease progression per RECIST; May be performed up to 14 days before the visit.
 O - PBMC and ctDNA tubes are included in the same kit but are separate tubes. Collection is done on D1 of C1-3 only.
 Reminder: Investigator can perform unscheduled labs, ECGs and physical exams as needed / clinically indicated

EXPANSION GROUP 2: UNRESECTABLE STS (5 DAY)

| Study Day | Screening | Treatment | | | | SFTY FU | LTFU | | |
|-----------|-------------------------------|-------------------|--------------------------------|--------------|-----------------------------------|----------------|-----------------------|--|--|
| | | Week 1 | | Week 2 | | | | | |
| | | Day -28 to Day -1 | Day 1 ^A | Day 2/3/4 | Day 5 | | | | |
| | On-Site | On-Site | On-Site | On-Site | Telephone or On-Site ^B | On-site | Variable ^M | | |
| Screening | Informed consent ^C | X | | | | | | | |
| | Medical history | X | | | | | | | |
| | Review Inc/Exc Criteria | X | | | | | | | |
| | Confirm Eligibility | | X | | | | | | |
| Safety | Physical Exam | X | | | | | | | |
| | Symptom-Directed PE | | X ^D | | | X | | | |
| | Vital Signs | X | X | X | X | X | | | |
| | ECHO or MUGA | X | Every other cycle ^E | | | X ^K | | | |
| | Triplecate 12-Lead ECG | X | X ^{D, F} | Cycle 1 Only | Cycle 1 Only | X | | | |
| | ECOG | X | Cycle 2+ | | | X | | | |
| | AE Review | | X | X | X | X | X | | |

Shasqi, Inc
SQ3370-001 Amendment 8 (Phase 2a Dose Expansion)

Statistical Analysis Plan
Version: 0.1 (Dated zzJUL2023)

| | | | | | | | | |
|----------|-----------------------------|----------------|---------------------------------|--------------|---|---------------------------|----------------|----------------|
| | Conmed Review | X | X | X | X | X | X | |
| Labs | Hematology & Chemistry | X | X ^D | Cycle 1 Only | X | Cycle 1 Only ^D | X ^D | |
| | Coagulation & Urinalysis | X | | | | | X ^D | |
| | Pregnancy Test | X ^G | X ^D | | | | X ^D | |
| | Serology | X | | | | | | |
| | Plasma PK | | See Separate PK Schedule | | | | | |
| | PBMC/ ctDNA | | Cycle 1, 2, 3 ^O | | | | | |
| | Cardio Tox Biomarkers | | Every other cycle ^E | | | | X | |
| | Tumor Biopsy | | Cycle 1, 2, 3 only ^H | | | | | |
| IP | CT / MRI & RECIST | X | Every 6 weeks ^I | | | | X ^L | X ^N |
| | Administer SQL70 Biopolymer | | X | | | | | |
| | Administer SQP33 Prodrug | | X ^J | X | X | | | |
| Survival | Vital Status | | | | | | | X |

Notes For EXPANSION GROUP 2: UNRESECTABLE STS (5 DAY)

A - Day 1-5 is typically Monday through Friday, however if the site can accommodate protocol procedures on the weekends Day 1 may start on any day of the week.

B - Day 10 visit may be performed via telephone (using a lab closer to a patient's home) or on-site.

C - Written informed consent must be obtained prior to any study-specific procedures.

D - May be performed up to 3 days before the visit.

E - ECHO/MUGA to be performed every other cycle starting at Cycle 3; may be performed up to 7 days before the visit. Serum sample for cardiotoxicity biomarker analysis is to be collected on the same day.

F - ECG to be performed pre dose and post dose +30minutes.

G - To be collected \leq 7 days prior to Cycle 1 Day 1 for women of child-bearing potential.

H - Collect optional biopsy unless the tumor is considered too small to be biopsied; biopsy can be performed during screening and up to 4 days prior to Day 1 for other cycles.

I - May be performed up to 7 days prior to the projected every 6 weeks from C1D1 date.

J - SQP33 prodrug infusion occurs within 3 hrs \pm 30 mins after receiving SQL70 biopolymer injection.

K - ECHO or MUGA not required at the Safety Follow-Up visit if performed in the previous 14 days.

L - CT / MRI & RECIST not required at the Safety Follow-Up visit if performed in the previous 6 weeks.

M - Capture and report next line of therapy x1 then for up to 2 years after treatment end; collected during routine clinic visits, telephone or e-mail with the subjects/caregivers or referring physician offices.

N - Until disease progression per RECIST; May be performed up to 14 days before the visit.

O - In addition to Day 1 of Cycles 1, 2, and 3, plasma samples should be taken at the time of the CT / MRI scans for RECIST between Cycles 4 -12 (see footnote I). PBMC and ctDNA tubes are included in the same kit but are separate tubes.

Reminder: Investigator can perform unscheduled labs, ECGs and physical exams as needed / clinically indicated

EXPANSION GROUP 3: HEAD AND NECK

| Study Day | Screening | Treatment | | | | SFTY FU | LTFU |
|-----------|-------------------------------|--------------------|---------------------------------|--------------|--------------------------------------|---------------------------|-----------------------|
| | | Week 1 | | | Week 2 | | |
| | | Day 1 ^A | Day 2 / 3 / 4 | Day 5 | Day 10 ± 2 days | | |
| Screening | On-Site | On-Site | On-Site | On-Site | Telephone or On-Site ^B | On-site | Variable ^M |
| | Informed consent ^C | X | | | | | |
| | Medical history | X | | | | | |
| | Review Inc/Exc Criteria | X | | | | | |
| Safety | Confirm Eligibility | | X | | | | |
| | Physical Exam | X | | | | | |
| | Symptom-Directed PE | | X ^D | | | X | |
| | Vital Signs | X | X | X | X | X | |
| | ECHO or MUGA | X | Every other cycle ^E | | | X ^K | |
| | Triplett 12-Lead ECG | X | X ^{D, F} | Cycle 1 Only | Cycle 1 Only | X | |
| | ECOG | X | Cycle 2+ | | | X | |
| | AE Review | | X | X | X | X | |
| Labs | Conmed Review | X | X | X | X | X | |
| | Hematology & Chemistry | X | X ^D | Cycle 1 Only | X | Cycle 1 Only ^D | X ^D |
| | Coagulation & Urinalysis | X | | | | | X ^D |
| | Pregnancy Test | X ^G | X ^D | | | | X ^D |
| | Serology | X | | | | | |
| | Plasma PK | | See Separate PK Schedule | | | | |
| | PBMC / ctDNA | | Cycle 1, 2, 3 ^O | | | | |
| | Cardio Tox Biomarkers | X | Every other cycle ^E | | | X | |
| IP | Tumor Biopsy | | Cycle 1, 2, 3 only ^H | | | | |
| | CT / MRI & RECIST | X | Every 6 weeks ^I | | | X ^L | X ^N |
| | Administer SQL70 Biopolymer | | X | | | | |
| Survival | Administer SQP33 Protodrug | | X ^J | X | X | | |
| | Vital Status | | | | | | X |

Notes For EXPANSION GROUP 3A: HEAD AND NECK

A - Day 1-5 is typically Monday through Friday, however if the site can accommodate protocol procedures on the weekends Day 1 may start on any day of the week.

B - Day 10 visit may be performed via telephone (using a lab closer to a patient's home) or on-site.

C - Written informed consent must be obtained prior to any study-specific procedures.

D - May be performed up to 3 days before the visit.

E - ECHO/MUGA to be performed every other cycle starting at Cycle 3; may be performed up to 7 days before the visit. Serum sample for cardiotoxicity biomarker analysis is to be collected on the same day.

F - ECG to be performed pre dose and post dose +30 minutes.

G - To be collected \leq 7 days prior to Cycle 1 Day 1 for women of child-bearing potential.

H - Collect optional biopsy unless the tumor is considered too small to be biopsied; biopsy can be performed during screening and up to 4 days prior to Day 1 for other cycles.

I - May be performed up to 7 days prior to the projected every 6 weeks from C1D1 date.

J - SQP33 protodrug infusion occurs within 3 hrs \pm 30 mins after receiving SQL70 biopolymer injection.

K - ECHO or MUGA not required at the Safety Follow-Up visit if performed in the previous 14 days.

L - CT / MRI & RECIST not required at the Safety Follow-Up visit if performed in the previous 6 weeks.

M - Capture and report next line of therapy x1 then for up to 2 years after treatment end; collected during routine clinic visits, telephone or e-mail with the subjects/caregivers or referring physician offices.

N - Until disease progression per RECIST; May be performed up to 14 days before the visit.

O - In addition to Day 1 of Cycles 1, 2, and 3, plasma samples should be taken at the time of the CT / MRI scans for RECIST between Cycles 4 -12 (see footnote I). PBMC and ctDNA tubes are included in the same kit but are separate tubes.

Reminder: Investigator can perform unscheduled labs, ECGs and physical exams as needed / clinically indicated.

